### 3.6 Randomization Procedures

There will be no randomization. After enrolling six (6) subjects into cohort A as per Section 5.1, enrollment will proceed concurrently into the remaining treatment cohorts.

### 3.7 Study Timeline (Primary Completion)

Each cohort is expected to reach primary completion 36 months after opening to accrual..

## 4 Study Drugs

### 4.1 Description, Supply and Storage of Investigational Drugs

#### 4.1.1 Pembrolizumab

Details on the preparation and administration of pembrolizumab are provided in the Pharmacy Manual. Refer to the package insert for complete information. Refer to the IB for additional information on pembrolizumab.

##### Classification

PD-L1 inhibitor, immunotherapy

##### Mechanism of Action

Pembrolizumab (MK-3475) is a potent humanized IgG4 mAb with high specificity of binding to the PD-1 receptor, thus inhibiting its interaction with PD-L1 and PD-L2. Based on preclinical in vitro data, pembrolizumab has high affinity and potent receptor blocking activity for PD-1. For more details, see Section 1.2.1 and the IB.

##### Contraindications

Immunodeficiency, autoimmune diseases requiring treatment with disease modifying agents, corticosteroids or immunosuppressive drugs, active infections.

##### Availability

Pembrolizumab will be provided to subjects enrolled on this study by Merck.

##### Handling, Storage, and Accountability

The investigator or designee must confirm appropriate temperature conditions have been maintained during transit for all study treatment received and any discrepancies are reported and resolved before use of the study treatment.

Only subjects enrolled in the study may receive study treatment and only authorized site staff may supply or administer study treatment. All study treatments must be stored in a secure, environmentally controlled, and monitored (manual or automated) area in accordance with the labeled storage conditions with access limited to the investigator and authorized site staff.

The investigator, institution, or the head of the medical institution (where applicable) is responsible for study treatment accountability, reconciliation, and record maintenance (i.e., receipt, reconciliation, and final disposition records).

For all trial sites, the local country Merck personnel or designee will provide appropriate documentation that must be completed for drug accountability and return, or local discard and destruction if appropriate. Where local discard and destruction is appropriate, the investigator is responsible for ensuring that a local discard/destruction procedure is documented.

The trial site is responsible for recording the lot number, manufacturer, and expiry date for any locally purchased product as per local guidelines unless otherwise instructed by Merck.

The investigator shall take responsibility for and shall take all steps to maintain appropriate records and ensure appropriate supply, storage, handling, distribution and usage of study treatments in accordance with the protocol and any applicable laws and regulations.

Clinical Supplies will be provided by Merck, as summarized in Table 2.

**Table 2 Product Descriptions**

Product Name & Potency	Dosage Form
Pembrolizumab 100 mg/4 mL	Solution for Injection

#### Clinical Supplies Disclosure

This trial is open-label; therefore, the subject, the trial site personnel, Merck and/or designee are not blinded to treatment. Drug identity (name, strength) is included in the label text; random code/disclosure envelopes or lists are not provided.

#### **4.1.2 Axitinib**

Please refer to the prescribing information for information and administration of the drug.

#### Classification

VEGF-targeting TKI

#### Mechanism of Action

Axitinib is a TKI indicated for the treatment of advanced RCC after failure of one prior systemic therapy. It inhibits multiple receptor tyrosine kinases, including VEGFR-1, VEGFR-2, and VEGFR-3.

#### Contraindications

There are no specific contraindications listed in the manufacturer's United States labeling.

#### Availability

Commercial supply of axitinib will be provided to subjects on this study by UCSF.

### Storage and Handling

The investigator shall assume responsibility for and shall take all steps to maintain appropriate records and ensure appropriate supply, storage, handling, distribution and usage of investigational product in accordance with the protocol and any applicable laws and regulations.

Axitinib is available as 1 mg and 5 mg tablets.

### Clinical Supplies Disclosure

This trial is open-label; therefore, the subject, the trial site personnel, Merck and/or designee are not blinded to treatment. Drug identity (name, strength) is included in the label text; random code/disclosure envelopes or lists are not provided.

### Returns and Reconciliation

The investigator is responsible for keeping accurate records of the amount dispensed to and returned by the subjects and the amount remaining at the conclusion of the trial.

Upon completion or termination of the study, all unused and/or partially used investigational product will be destroyed at the site per institutional policy. It is the Investigator's responsibility to arrange for disposal of all empty containers, provided that procedures for proper disposal have been established according to applicable federal, state, local and institutional guidelines and procedures, and provided that appropriate records of disposal are kept.

## **4.2 Drug Accountability**

The Investigational Pharmacist will manage drug accountability records.

## **4.3 Drug Ordering**

UCSF will obtain pembrolizumab directly from Merck as study supply. Commercial drug will be supplied by UCSF.

Axitinib will be obtained as commercial supply.

## **4.4 Packaging and Labeling of Study Drugs**

Study drugs will be labeled by sponsor prior to receipt at UCSF. Prior to administration or dispensing of drug, UCSF Investigational Drug Pharmacy will affix an appropriate clinical label with patient identifiers per UCSF institutional standards, adhering to applicable local and federal laws.

## **5 Treatment Plan**

### **5.1 Dosage and Administration**

In all subjects, pembrolizumab will be administered as a flat dose of 200 mg for 3 cycles prior to surgery and 400 mg for 9 or 18 cycles after surgery, as an IV infusion. The Pharmacy manual

contains specific instructions for the preparation of pembrolizumab infusion fluid as well as the administration of the infusion solution.

On Day 1 of each cycle, pembrolizumab will be administered once as a 30-minute IV infusion. Every effort will be made to keep infusion timing as close to 30 minutes as possible. However, given the variability of infusion pumps, a window of -5 minutes and +10 minutes is permitted (i.e. infusion time is 30 minutes: -5 min/+10 min).

The treatment to be used during the study is outlined below in Table 3 and Table 4.

**Table 3 Neoadjuvant Treatment Regimen Per Cohort**

Cohort	Drug/Dose	Dose Frequency	Route of Administration	Schedule	Dose Levels
A/B/C	Pembrolizumab 200 mg	Q3W	IV	Day 1 of each 21-day cycle (Q3W)	N/A
B	Axitinib 5 mg titratable	BID	PO	Days 1-21 of each 21-day cycle	DL -2: 1 mg BID DL -1: 3 mg BID DL 1: 5 mg BID DL 2: 7 mg BID DL 3: 10 mg BID
C	TBD (agent to be determined)	TBD	TBD	TBD	TBD

Abbreviations: BID = twice daily; DL = dose level; IV = intravenous; N/A = not applicable; PO = by mouth; Q3W = every 3 weeks; TBD = to be determined

**Table 4 Adjuvant Treatment Regimen Per Cohort**

Cohort	Drug/Dose	Dose Frequency	Route of Administration	Schedule	Dose Levels
A/B/C	Pembrolizumab 400 mg	Q6W	IV	Day 1 of each 42-day cycle (Q6W)	N/A
B	Axitinib 5 mg titratable	BID	PO	Days 1-42 of each 42-day cycle	DL -2: 1 mg BID DL -1: 3 mg BID DL 1: 5 mg BID

Cohort	Drug/Dose	Dose Frequency	Route of Administration	Schedule	Dose Levels
					DL 2: 7 mg BID DL 3: 10 mg BID
C	TBD (agent to be determined)	TBD	TBD	TBD	TBD

Abbreviations: BID = twice daily; DL = dose level; IV = intravenous; N/A = not applicable; PO = by mouth; Q6W = every 6 weeks; TBD = to be determined.

### 5.1.1 Cohort A: Pembrolizumab Monotherapy

Up to twelve subjects will be enrolled into Cohort A. The first 6 subjects accrued to Cohort A will be evaluated in a safety lead-in for the safety of pembrolizumab prior to planned CN/MET. After six (6) subjects are enrolled into Cohort A, the pembrolizumab-based combination cohorts will open to concurrent enrollment.

Administer pembrolizumab doses according to Table 3 and Table 4. See section 5.2 for details regarding dose modifications and dosing delays.

During neoadjuvant treatment, subjects will receive 3 cycles of pembrolizumab (200 mg Q3W), given on Day 1 of each 21-day cycle. Of particular interest are surgical complications (Appendix 3). For the first 6 patients in the safety lead-in, if  $\geq 2$  subjects experience Grade IV and V surgical complications according to the Clavien-Dindo classification (Appendix 3), or if  $\geq 2$  subjects experience a delay in surgery beyond the specified 14-21 day window following the end of the preoperative treatment period (that is, 14-21 days from Cycle 3, Day 21; delays for scheduling, operating room scheduling or patient preference are not included), the study will be halted to accrual. Given the complexity of surgery, it will be difficult to attribute surgical complications to the preoperative administration of pembrolizumab. Thus, the occurrence of these events may not require an early end to the study, but will be discussed amongst the members of the Joint Steering Committee, Merck, and the Sponsor to determine whether study can re-open to accrual.

### 5.1.2 Cohort B: Pembrolizumab + Axitinib

#### 5.1.2.1 Safety Lead-In

The first 6 subjects accrued to Cohort B will be evaluated to test the safety of the combination of pembrolizumab and axitinib. All 6 subjects in Cohort B will be followed for 28 days after surgery for excessive post-operative complications before additional subjects are enrolled to each combination cohort. If  $\leq 1$  subject experience Grade IV/V surgical complications per the Clavien-Dindo classification (Appendix 3), then 11 additional evaluable subjects will be accrued to the cohort. If  $\geq 2$  subjects experience Grade IV/V surgical complications, or if  $\geq 2$  subjects experience a delay in surgery beyond the specified 14-21 day window following the end of the preoperative treatment period (that is, 14-21 days from Cycle 3, Day 21; delays for scheduling, operating room scheduling or patient preference are not included), then the cohort will be halted to accrual, and the safety data reviewed to modify the protocol as appropriate, including changes in dose level

(Section 5.1). If the cohort is re-opened with a change in dose level, an additional 6 subjects will be accrued to evaluate safety. If  $\leq 1$  subject experience a Grade IV/V surgical complication, then 11 additional subjects will be accrued to the cohort at the reduced dose. If  $\geq 2$  subjects experience a Grade IV/V surgical complication, the cohort will be terminated for lack of safety. Therefore, a minimum of 4, and a maximum of 36 subjects may be accrued into Cohort B.

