## 8.2 Determination of Sample Size and Accrual Rate

### 8.2.1 Sample Size and Power Estimate

For the primary objective, there will be a binary classification. A subject will be considered to have a “positive response” if there is a  $\geq 2$ -fold increase (from pre- to post-treatment) in the number of TICCs, and a “negative response” if there is  $< 2$ -fold increase.

For Cohort A, with 12 subjects, if the true response rate is 30%, the 90% confidence interval of the response rate is (8%, 52%).

For each of the combination cohorts (cohorts B and C), the expanded part will be accrued based on group sequential design. In the first stage, 12 subjects (including the 6 subjects in safety lead-in) will be accrued at the dose level decided at safety lead in. If there are one or fewer responses in these 12 subjects, the study will be stopped due to futility, and if there are 5 or more responses,

the study will be stopped due to efficacy (one-sided alpha spending =0.0004). The final decision to terminate the cohort or continue accruing after these first 12 subjects will be based on discussion amongst members of the Joint Steering Committee, which is comprised of representatives for both Merck and the Sponsor. If accrual to the cohort is continued, additional subjects will be accrued for up to 36 evaluable subjects (or up to 30 if no dose reductions occur).

The null hypothesis of a 10% response rate will be rejected if 6 or more responses are observed in 30 subjects. This design yields a one-side type I error rate of 0.05 and power of 82.3% when the true response rate is 30%. Additionally, the first 6 subjects will be considered the “safety lead-in” for each cohort. If there are  $\geq 2$  DLTs in these first 6 subjects, then dose reduction will proceed as described in Section 5.1 and an additional 6 subjects will be accrued. The 6 subjects accrued as the safety lead-in are evaluable. Therefore, a minimum of 4, and a maximum of 36 subjects will be accrued to each pembrolizumab-based combination cohort.

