## 8.3 Interim Analyses and Stopping Rules

Each cohort will be stopped early for lack of safety, if the safety lead-in portion cannot be completed as outlined in the Study Design (Section 3).

The planned interim analysis for both futility and efficacy will be included based on group sequential design for the combination cohorts. 12 subjects (including the 6 subjects in safety lead-in) will be accrued at the dose level decided at safety lead-in. If there are one or fewer responses in these 12 subjects, the study will be stopped due to futility, and if there are 5 or more responses, the study will be stopped due to efficacy (one-sided alpha spending =0.0004). The final decision to terminate the cohort or continue accruing after these first 12 subjects will be based on discussion amongst members of the Joint Steering Committee, which is comprised of representatives for both Merck and the Sponsor.

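### Section 5.1.2.1 tells the team to add 11 Cohort B subjects after a passed lead-in, which fits neither the 12-then-30/36 design in Section 8 nor the paragraph's own maximum of 36

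*Combined protocol and SAP*

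**What the plan says.** Section 5.1.2.1 sets out the Cohort B lead-in. Six subjects are treated, and "All 6 subjects in Cohort B will be followed for 28 days after surgery" before enrolment goes further. If at most one has a Grade IV/V surgical complication, "then 11 additional evaluable subjects will be accrued to the cohort". If the lead-in fails, accrual halts for review. If the cohort re-opens at a changed dose level, a second group of 6 is assessed and, if that group passes, "then 11 additional subjects will be accrued to the cohort at the reduced dose". The paragraph concludes: "Therefore, a minimum of 4, and a maximum of 36 subjects may be accrued into Cohort B".

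The statistical section counts differently. Section 8.2.1 states: "In the first stage, 12 subjects (including the 6 subjects in safety lead-in) will be accrued". It confirms that "The 6 subjects accrued as the safety lead-in are evaluable". It sets futility and efficacy bounds at 12 and provides that, if the cohort goes on, "additional subjects will be accrued for up to 36 evaluable subjects (or up to 30 if no dose reductions occur". Its final rejection rule is written for 30 subjects. Section 8.3 repeats the 12-subject look and gives the Joint Steering Committee "The final decision to terminate the cohort or continue accruing after these first 12 subjects".

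Section 3.2 allows up to 36 evaluable subjects per combination cohort and 84 in the study, and refers to Section 8.2.1 for the sample size. The Abstract gives the same 84 and the range of 4 to 36 per combination cohort. Section 8.1.1 applies the group sequential design after each lead-in.

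**The concern.** Section 5.1.2.1 is where the study team reads how many subjects to enrol once the lead-in has passed, and Cohort B is the only combination cohort with a defined regimen. The paragraph gives a definite count, does not mention the decision at 12, and does not refer to Section 8.2.1 or 8.3. Staff working from Section 5 and staff working from Section 8 would have different accrual targets and different pause points for the same cohort.

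The paragraph also presents 36 as the consequence of its own steps, and those steps do not lead there.

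**Working it through.** **Inputs**

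- Section 5.1.2.1: lead-in 6; second lead-in 6 after a dose change; 11 further subjects after either; range 4 to 36.
- Sections 8.2.1 and 8.3: first stage 12, including the 6 lead-in subjects.
- Section 8.2.1: ceiling 30 without a dose reduction, 36 with one.
- Section 8.2.2: up to 2 replacements.
- Section 3.2 and Abstract: up to 12 in Cohort A, up to 36 per combination cohort, up to 84 in all.

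**Reproducing the maximum of 36**

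- From Section 5.1.2.1, no dose change: 6 + 11 = 17.
- From Section 5.1.2.1, with a dose change: 6 + 6 + 11 = 23.
- Adding both replacements: 17 + 2 = 19 and 23 + 2 = 25.
- From Section 8.2.1: 6 at the first dose level + 30 = 36.

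The 36 is reproduced from Section 8 only.

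**Accrual still to come after a passed lead-in**

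| | Section 5.1.2.1 | Section 8 |
|---|---|---|
| To the interim | not mentioned | 12 − 6 = 6 |
| After the interim | not mentioned | up to 30 − 12 = 18 |
| Total after the lead-in | 11 | up to 6 + 18 = 24 |

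Eleven equals none of 6, 18 or 24.

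**Size of the mismatch**

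- Past the interim: 17 − 12 = 5 subjects.
- Below the ceiling, no dose change: 30 − 17 = 13.
- Below the ceiling, with a dose change: 36 − 23 = 13.
- Study total: 12 + 36 + 36 = 84, as stated. With Cohort B at 23 and Cohort C assumed to reach its ceiling: 12 + 23 + 36 = 71.

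**The minimum of 4**

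One completed lead-in gives 6. A total of 4 arises if each of two lead-ins closes at its second event (2 + 2 = 4). Neither Section 5.1.2.1, Section 8.2.1 nor the Abstract states that derivation.

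**Check of the correction**

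- No dose change: 6 + 6 + 18 = 30.
- With a dose change: 6 + 6 + 6 + 18 = 36.

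Both agree with Section 8.2.1.

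**The case against.** The strongest reply is that Section 8 governs. Section 3.2 refers to Section 8.2.1, Section 8.1.1 applies the group sequential design after the lead-in, and 30 and 36 are ceilings, not targets. Section 5.1.2.1 does not say that accrual closes after the 11, so the number could be a partial tranche, with 36 still the correct maximum. That limits the consequence: the interim is not cancelled and the final size is not changed. It does not rescue the figure. No stage of the design ends at 17 or 23, the paragraph says nothing of a tranche, and it offers its steps as the reason for 36.

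The overrun of 5 may also cost nothing in practice. Section 8.3 states no accrual hold. Section 8.2.3 expects about 2 subjects a month, and Table 7 puts surgery at week 12. If all accrual went to Cohort B (an assumption), 12 weeks is about 2.8 months, and 2.8 × 2 is between 5 and 6 subjects enrolled while the twelfth subject reaches surgery. This stands: the 5 is what the text orders past the decision point, not an estimate of avoidable enrolment.

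The minimum of 4 can be read as 2 + 2, and it appears consistently in three places. That makes it a missing derivation, not a proven contradiction. The 71 depends on an assumption about Cohort C and only illustrates the gap.

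Lastly, operational risk is contained. This is a single-centre study, the Data and Safety Monitoring Committee authorises enrolment past the lead-in (Appendix 2), and the Joint Steering Committee decides at 12. These safeguards reduce the chance of harm, but they leave the wrong number in the treatment plan.

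**Conclusion.** The concern holds. The count of 11 in Section 5.1.2.1, given twice, disagrees with Sections 8.2.1 and 8.3, where a passed lead-in is followed by 6 subjects to the interim and up to 18 after it. It also disagrees with the maximum in its own paragraph: the steps reach 17 or 23, each 13 below the ceiling for that branch.

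This rests only on figures in the protocol. No effect on power or type I error follows, because Section 8 continues to define the interim and the final analysis. The alpha-spending, type I error and power figures quoted there are a separate question. The point should be fixed because a current accrual instruction is wrong as written and the correction is simple. The minimum of 4 is a secondary point that needs an explanation.

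**What to change.** In Section 5.1.2.1, replace both statements of 11 with accrual that follows Section 8: 6 more evaluable subjects to reach 12 at the dose level in use, the interim decision under Section 8.3, then up to 18 more to reach 30. State that this gives at most 30 without a dose change and 36 with one, and cross-refer to Sections 8.2.1 and 8.3. If the stage sizes in Section 8 are ever revised, the numbers in Section 5.1.2.1 must be revised with them.

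Reconcile the minimum of 4 with the 6-subject lead-in, or state how it is derived, and use the same wording in the Abstract, Section 5.1.2.1 and Section 8.2.1.

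The cost is an edit to one paragraph, a cross-reference, and matching wording for the minimum in the two other places. No subjects, visits or analyses are added, since 30, 36 and 84 are already in the protocol.

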### 5.1.2.2 Treatment Plan

Administer pembrolizumab and axitinib doses according to Table 3 and Table 4. On Day 1 of each cycle, administer axitinib after the subject completes their pembrolizumab infusion. Axitinib may be administered as soon as the pembrolizumab infusion is completed. Additional details regarding the treatment plan are provided below.

#### **Preoperative treatment period (3 cycles):**

Subjects will begin treatment with pembrolizumab 200 mg Q3W, administered on Day 1 of each 21-day cycle. Axitinib will be self-administered twice daily. After 3 cycles of therapy, subjects will have a 2-week treatment break prior to CN and/or MET.

During the preoperative treatment period, subjects who experience toxicities requiring study discontinuation will proceed immediately to CN and/or MET, as soon as it is determined to be safe and feasible per the treating physicians and PI. Subjects who experience toxicities requiring dose delays must be able to resume treatment within 42 days of the prior dose of pembrolizumab. Subjects unable to resume treatment within 42 days of the prior dose of pembrolizumab must discontinue treatment participation.

#### **CN/MET:**

CN/MET will be performed per institutional standard of care, 14 to 21 days following the end of the preoperative treatment period (14-21 days from Cycle 3, Day 21).

#### **Post-CN/MET treatment:**

Following CN/MET (or continued therapy in metastatic subjects who achieve CR during the preoperative treatment period), subjects will be offered the option to continue treatment on study as summarized in Section 3.1 (see Section 6.3 for exceptions).

The first dose of post-CN/MET therapy will be no sooner than 21 days, and no later than 42 days, following CN/MET, based on adequate postoperative recovery (including wound healing), as assessed by the treating physicians. Subjects with metastatic disease who achieve CR during the preoperative treatment period (obviating the need for metastasectomy) will continue with their pembrolizumab-based therapy without a break allowing for surgery and recovery. Subjects will receive pembrolizumab 400 mg Q6W, administered on Day 1 of each 42-day cycle.

- In subjects who continue on the combination of pembrolizumab and axitinib as continued therapy following CN/MET (or following CR during preoperative therapy in metastatic patients), axitinib dose-titration (as well as dose modification and delays) should be managed by the treating physician per standard of care.

- Subjects treated with the combination of pembrolizumab and axitinib may experience AEs attributable to axitinib that require holding or discontinuing axitinib. Dose delays or discontinuation of axitinib should be managed per standard of care. In cases where axitinib must be discontinued permanently due to toxicity, subjects may remain on study and receive pembrolizumab monotherapy. In cases where axitinib is held due to toxicity:
  - Subjects who resume axitinib within 42 days may continue to receive combination therapy
  - Subjects who do not resume axitinib within 42 days may remain on study and receive pembrolizumab monotherapy (400 mg Q6W), and axitinib must be discontinued for the remainder of the study duration
  - Subjects treated with the combination of pembrolizumab and axitinib may also experience AEs attributable to pembrolizumab that require holding or discontinuing pembrolizumab. Dose delays, modifications, and discontinuations are discussed in Section 5.2. In cases where pembrolizumab must be discontinued due to toxicity, subjects may remain on study and receive axitinib monotherapy. In cases where pembrolizumab is held due to toxicity:
    - Subjects who resume adjuvant pembrolizumab within 42 days may continue to receive combination therapy; subjects will begin treatment with pembrolizumab 400 mg Q6W, administered on Day 1 of each 42-day cycle. The total duration of adjuvant pembrolizumab (either 9 cycles for R0/R1 resection, or 18 cycles for R2 resection) reflects the total number of pembrolizumab doses administered, even if doses are withheld for toxicity and then pembrolizumab is resumed. Subjects who do not resume adjuvant pembrolizumab within 42 days may remain on study and receive axitinib monotherapy, and pembrolizumab must be discontinued for the remainder of the study duration

